9.1.1. Incidence of Adverse Events

All AEs, including SAEs, will be presented in data listings.

Summaries of the total number of TEAEs, the number of subjects with at least one TEAE and the incidence will be presented by dose group. The number of subjects, the number of events and the incidence will also be presented by system organ class (SOC) and preferred term (PT). At each level of summarization, a subject is counted once if the subject reported one or more events.

9.1.2. Relationship of Adverse Events to Study Drug

A summary of TEAEs by relationship to study drug will be presented by dose group in a table. The investigator will provide an assessment of the relationship of the event to the study drug. The possible relationships are “Not Related”, “Unlikely”, “Possible”, and “Related”. In the TEAE relationship table, if a subject reported multiple occurrences of the same TEAE, only the most closely related occurrence will be presented. TEAEs that are missing a relationship or with a relationship other than “Not Related” or “Unlikely” will be presented in the summary table as “Related” but will be presented in the data listing with a missing relationship or the actual relationship respectively. Percentages will be based on the number of subjects within each dose group in the safety analysis set.

9.1.3. Severity of Adverse Event

A summary of TEAEs by severity will be presented by dose group in a table. The severity that will be presented represents the most extreme severity captured on the case report form (CRF) page. The possible severities are “Mild”, “Moderate”, “Severe”, “Life-threatening” and “Death”. In the TEAE severity table, if a subject reported multiple occurrences of the same TEAE, only the most severe will be presented. Treatment-emergent AEs that are missing severity will be presented in tables as “Severe” but will be presented in the data listing with a missing severity. Percentages will be calculated out of the number of subjects within each dose group in the safety analysis set.

9.1.4. Toxicity Grade of Adverse Event

A summary of TEAEs by toxicity grade (per protocol APPENDIX A3: TOXICITY SCALE) will be presented by dose group in a table. If a subject reported multiple occurrences of the same TEAE, only the highest grade will be presented. Treatment-emergent AEs that are missing grade will be presented in tables as Grade 4 but will be presented in the data listing with a missing toxicity grade. Percentages will be calculated out of the number of subjects within each dose group in the safety analysis set.

9.1.5. Serious Pre-dosing Adverse Events

A serious pre-dosing adverse event is any event that meets the criteria for SAE reporting and occurs after the subject signs the ICF, but before infusion of PF-06838435. Serious pre-dosing events will be presented in a data listing.

9.1.6. Serious Adverse Events

Any AE reported as resulting in death, immediate risk of death (life threatening), inpatient hospitalization or prolongation of existing hospitalization, persistent or significant disability/incapacity, or a congenital/anomaly/birth defect will be classified as a serious adverse event (SAE). An SAE may also be any other medically important event that, in the opinion of the Investigator, may jeopardize the subject or may require intervention to prevent one of the other outcomes listed above. In addition, any suspected transmission via a medicinal product of an infectious agent is also considered an SAE.

Serious treatment-emergent adverse events (SAEs) will be categorized and presented by dose group in a table by SOC and PT in a manner similar to that described in Section 9.1.1. Treatment-emergent SAEs with relationship to study drug will also be presented in a table. A treatment-related treatment-emergent SAE is a treatment-emergent SAE with any relation to study drug other than “Not Related” or “Unlikely”. Treatment-emergent SAEs that are missing a relationship will be presented in the table as “Related” but will be presented in the data listing with a missing relationship. At each level of summarization, a subject is counted once if reporting one or more events. Percentages will be calculated out of the number of subjects within each dose group in the safety analysis set.

9.1.7. Death

All subject deaths during the study will be listed. Deaths will be identified from the AE with “Outcome” recorded as “Fatal” on the AE eCRFs.

9.2. Clinical Laboratory Evaluations

For laboratory evaluations, baseline is defined as the last non-missing evaluable assessment taken prior to PF-06838435 infusion. Post-baseline laboratory results are defined as any assessment taken after the infusion of PF-06838435.

Laboratory assessments will be performed by a certified laboratory. All summaries will be based on the units provided by the central laboratory, conversion for the local labs will be performed to make the units consistent with the central laboratory results. Summary tables will use central laboratory results. Both central and local results will be included in listings.

Additional laboratory tests other than the tests listed below will be performed to assess the safety of the immunosuppressive therapy regimen, if implemented.

Laboratory parameters of thrombotic potential in any individual who reaches >150% vector-derived FIX:C activity levels after PF-06838435 infusion will be summarized by dose group and listed in a similar way for all the below analysis.

The cases of t-cell response will be described by narrative.

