13. LFTs – albumin, total bilirubin, direct bilirubin, indirect bilirubin, alkaline phosphatase (ALP), aspartate aminotransferase (AST), alanine aminotransferase (ALT), total protein, gamma-glutamyl transferase (GGT), and lactate dehydrogenase (LDH);

Immunology - CPT™ for PBMC by ELISPOT and PAXgene for RNA. PAXgene samples will be stored for analysis at the end of study.

14. Hepatic transaminases and FIX transgene expression will be monitored twice-weekly or thrice-weekly to detect early changes. Between Weeks 1 and 12 post-vector infusion, monitoring will include LFTs, FIX:C, FIX Ag, CPT™ for PBMC by ELISPOT and PAXgene for RNA. Spare plasma, from already collected blood samples will be stored for repeat or additional tests. Some participants may need more frequent monitoring using unscheduled visits.
15. Activated partial thromboplastin time (aPTT) measured in seconds; TAT will be taken just prior to the infusion of FIX product.
16. Participants should be advised to temporarily suspend prophylaxis regimen after vector infusion until being advised by the Investigator to resume.
17. At Day 0, participants should arrive at the clinic with at least 96 hours (4 days) washout of pd-FIX/rFIX or up to 168 hours (7 days) washout of extended half-life FIX product. Participants will receive a single IV infusion of 100 IU/kg of FIX protein product over 10 (±2) minutes.
18. Blood samples will be collected at pre-infusion, 10 (±2) minutes, 1 hour ± 10 minutes, 3 hours ± 10 minutes, 6 hours ± 10 minutes, and 24 (±1) hours from the start-of-infusion of FIX protein product.
19. Thromboelastography (TEG) and/or rotational thromboelastogram (ROTEM) – Only selected participants at selected sites capable of performing these tests locally.  
CCI  
Blood samples will be collected at pre-infusion and 10 (±2) minutes from the start-of-infusion of FIX protein product on Day 0 and End-of-Study Visits.
20. After the completion of FIX protein product infusion, participants will receive PF-06838435 infused via infusion pump over a period of approximately 60 minutes.
21. Haem-A-QoL, EQ-5D-5L, McGill pain questionnaire, and Hemophilia Activities List (including Changes in Level of Activity) questionnaires will be completed by the participants.  
CCI  
[REDACTED]
23. Immunomodulation See [Appendix 2](#): possible tests below:  
LFT – albumin, total bilirubin, direct bilirubin, indirect bilirubin, ALP, AST, ALT, total protein, GGT, and LDH;  
Coagulation –aPTT, FIX:C, FIX Ag  

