#### 4.1.4. FIX Incremental Recovery

FIX incremental recovery will be measured up to 24 ( $\pm 1$ ) hours post-infusion of FIX protein products to assess time at maximum activity and percent recovery for exogenous FIX activity. The exogenous FIX activity levels will be determined by one-stage clotting assay. Participants are required to have at least 96 hours of washout for pd- or r-FIX or up to approximately 168 hours of washout for extended half-life rFIX prior to FIX incremental recovery test on Dosing Day (Day 0).

FIX incremental recovery assessments will be conducted by collecting blood samples at various time-points up to 24 ( $\pm 1$ ) hours from the start of FIX protein product infusion. Blood samples on Day 0 will be collected pre-infusion, 10 ( $\pm 2$ ) minutes, 1 hour  $\pm 10$  minutes, 3 hours  $\pm 10$  minutes, 6 hours  $\pm 10$  minutes, and 24 ( $\pm 1$ ) hours from the start-of-infusion of FIX protein product.

Samples for thrombin generation assessments will also be collected on Day 0 at pre-infusion and 10 ( $\pm 2$ ) minutes from the start-of-infusion of FIX protein infusion and evaluated by an

CCI performed at the central laboratory. For participants at selected sites depending on the testing capabilities, additional samples for global hemostasis may also be collected at pre-infusion and 10 ( $\pm$ 2) minutes from the start-of-infusion of FIX protein infusion and evaluated by the whole blood TEG and/or rotational thromboelastogram (ROTEM) locally.

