**Table 3. Protocol-Required Laboratory Assessments**

Assessment	Description
Hematology (CL)	
 
• WBC count with Differential: 
 
○ Neutrophils
 
○ Lymphocytes
 
○ Monocytes
 
○ Eosinophils
 
○ Basophils
 
 
 
• RBC count
 
• Hemoglobin
 
• Hematocrit
 
• Platelet count
 

Clinical Chemistry (CL)	
 
• Sodium
 
• Potassium
 
• Chloride
 
• Bicarbonate
 
• Glucose
 
• Phosphate
 
• Serum creatinine
 
• BUN
 

Lipid Panel (CL)	
 
• LDL
 
• VLDL
 
• HDL
 
• Triglycerides
 
• Total Cholesterol
 

ABO (LL)	
 
• ABO group
 

Urinalysis (CL)	
 
• pH
 
• Specific Gravity
 
• Protein
 
• Blood
 
• Ketones
 
• Glucose
 

Liver Function Tests (LL and CL)	
 
• Albumin,
 
• Total bilirubin
 
• Direct bilirubin
 
• Indirect bilirubin
 
• ALP
 
• AST
 
• ALT
 
• Total protein
 
• GGT
 
• LDH
 

Liver Fibrosis (CL)	
 
• FibroTest/Fibrosure (if applicable)
 

Coagulation (LL, CL as noted)	
 
• FIX activity, aPTT (LL and CL)
 
• FIX antigen, INR, TAT, CCI (CL)
 
• ROTEM and/or TEG (LL where available)
 
• FIX inhibitor (Nijmegen Bethesda), (LL screening visit only, CL screening and all other visits)
 

AAV Neutralizing Antibody (CL)	
 
• PF-06838435 Neutralizing Antibody
 

Immunology (CL)	
 
• ELISPOT IFN-γ with PBMCs to assess cellular immune responses to AAV capsid and to FIX
 

CCI	

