9.2.2. Activation of Coagulation Parameters

Activation of coagulation parameters which include activated partial thromboplastin time (aPTT), INR, TAT, and TEG and/or ROTEM (at selected time-points for FIX incremental recovery assessment) result will be presented in a data listing and the actual and change from baseline will be summarized by dose group in a table. In addition, change from baseline will be summarized for all post-baseline visits. INR, TAT, TEG, and ROTEM are only collected in subjects with > vector-derived FIX:C activity levels >150% of normal are achieved.

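### SAP 9.2 limits laboratory tables to central results, so the TEG/ROTEM summary planned in SAP 9.2.2 has no eligible data, and a local liver result has no fallback role when its paired central result is missing

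*SAP*

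**What the plan says.** SAP 9.2 sets the data source for laboratory output: "Summary tables will use central laboratory results", and "Both central and local results will be included in listings". It adds that "conversion for the local labs will be performed to make the units consistent with the central laboratory results", but does not say that a converted local value may then enter a table.

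SAP 9.2.2 groups TEG and/or ROTEM with aPTT, INR and TAT and says that "the actual and change from baseline will be summarized by dose group in a table". Its last sentence restricts collection of INR, TAT, TEG and ROTEM to participants whose vector-derived FIX:C exceeds 150% of normal.

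The Protocol places TEG and ROTEM at the local laboratory each time it assigns them:
- Table 3 (LL is the local and CL the central laboratory): "ROTEM and/or TEG (LL where available".
- Schedule of Activities note 19: "Only selected participants at selected sites capable of performing these tests locally".
- Section 4.1.4: "evaluated by the whole blood TEG and/or rotational thromboelastogram (ROTEM) locally". Section 4.1.7.2 agrees.

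For liver tests Table 3 reads "Liver Function Tests (LL and CL". Appendix 2 calls for a local result when the central one would come too late for a dosing or response decision. It asks for a central sample at the same time, and requires the local value in the CRF if a decision rested on it. SAP 9.2.1 plans low/normal/high shift tables of liver tests at Week 52 and at the post-baseline minimum and maximum. Table 14.3.4.5 covers participants with a 1.5-fold transaminase rise over baseline. SAP 4 imputes nothing and keeps unscheduled visits out of tables.

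**The concern.** The source rule in SAP 9.2 is general, while the tests it governs come from different laboratories. For a test with no central result, the rule and the promised table cannot both be met, and the programmer would have to choose between leaving the summary empty and breaking the rule.

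For a test run at both laboratories, the SAP does not say what happens when the central result is absent but a local one is on record. Laboratory change is among the primary safety endpoints. Transaminases carry particular weight: a rise of about 1.5-fold is a criterion for corticosteroids (Protocol 4.1.5), and Grade III-IV elevations feed the rules that suspend enrolment (Protocol 4.3.1). A local value that led to action could therefore be missing from the worst-value tables.

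**Working it through.** The plan gives no figure to reproduce here. The check sets its rules side by side.

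**1. TEG/ROTEM**
- Records eligible for a table under SAP 9.2: central results only.
- Central TEG/ROTEM results under Protocol Table 3, note 19 and Sections 4.1.4 and 4.1.7.2: none, by design.
- Records available to the SAP 9.2.2 summary: 0 in every dose group. The baseline values are local too, so change from baseline is equally empty.
- The SAP table list does not settle the matter. Its coagulation titles (14.3.4.3.1 and 14.3.4.3.2) name aPTT, INR, TGA and TAT, so the TEG/ROTEM summary exists only in the text of 9.2.2.

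**2. When TEG/ROTEM are collected**
- Note 19: before and 10 (±2) minutes after the start of the FIX product infusion, on Day 0 and at End-of-Study, at capable sites.
- SAP 9.2.2, last sentence: only in participants above 150% vector-derived FIX:C.
- The Day 0 samples are taken before the vector is given, so they cannot depend on a vector-derived level. The same section of the SAP also ties TEG/ROTEM to the incremental recovery time points. These passages conflict whichever laboratory is used.

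**3. Liver tests: when a local value drops out**

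All of the following must hold:
- a local result is recorded for a draw;
- the paired central result is missing or unusable, not merely late, because a late result still reaches the database and the tables;
- the draw belongs to a scheduled visit, since unscheduled draws are already excluded by SAP 4;
- no other tabulated central value puts the participant in the same category.

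The local value is then listed but enters neither the maximum post-baseline shift nor Table 14.3.4.5, and nothing replaces it.

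**4. Direction**

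The maximum over a subset of values cannot exceed the maximum over all of them. With the baseline held fixed, dropping post-baseline values can lower the recorded peak or leave it unchanged, but never raise it. Any error in the maximum tables is therefore towards looking safer.

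**5. Size per participant affected**

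One misclassified participant moves a percentage by 1/n:
- n = 30 (upper figure in SAP 4.1): 1/30 = 3.3 points
- n = 20 (Protocol 9.2): 1/20 = 5.0 points
- n = 15 (SAP 3.1): 1/15 = 6.7 points
- n = 5 (one initial dose level): 1/5 = 20 points

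The documents give no rate of missing or unusable central results, so the expected number of such participants cannot be computed.

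**The case against.** Central-only tables are a legitimate choice for comparability in a multi-centre study. SAP 9.2.2 can be read as a specific exception to a general rule, since only local TEG/ROTEM values exist. These tests are optional, confined to selected sites, and listed in any case. This makes the matter one of wording, but the exception is not written, and no entry in the table list supplies it.

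On liver tests the objection goes further and largely stands. Appendix 2 asks for a simultaneous central sample, so loss needs a second failure. The information also appears elsewhere: local values are listed, Listing 16.2.5.3 covers corticosteroid and immunosuppressive use after transaminase rises, clinically significant changes are recorded as adverse events, T-cell responses get narratives, and per-subject FIX:C and LFT figures are planned. With about 20 participants and descriptive analysis only, a treated participant is unlikely to be hidden from the report.

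A reader might infer that participants with elevations could easily vanish from the tables. Suppose a share m of draws lacks a central result, independently of the value, and 5 participants have a rise. Then 1 − (1 − m)^5 is 22.6% at m = 5% and 41.0% at m = 10%. Neither input comes from the documents, and the formula gives the chance that at least one of five particular peak draws lacks a central result. It is not the chance that a participant leaves the tables. The SAP 9.2.1 shift is low/normal/high, and note 14 has transaminases monitored two or three times a week between Weeks 1 and 12, so any other tabulated value above the upper limit keeps the participant classed as high. On the same assumptions with two elevated draws each, 1 − (1 − m²)^5 is 1.2% to 4.9%. These figures only show how strongly the answer depends on the assumptions; neither range is an estimate for this trial.

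A reader might also infer that tables should take the worse of the central and local value whenever both exist. Nothing here supports that: the central result already fills the table, and taking the higher of two noisy readings would inflate apparent elevations.

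**Conclusion.** The TEG/ROTEM conflict is firm. SAP 9.2 and SAP 9.2.2 cannot both be followed, and under the stated rule the summary has n = 0 in every dose group. This rests only on the text of the two documents. The values would still be listed, so the loss is of the summary and not of the data.

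The liver point holds in a limited form. The SAP has no fallback when the central result paired with a recorded local one is missing or unusable. The direction of any resulting error is known (towards looking safer), its frequency is not, and one affected participant is worth 5 points at n = 20 or 20 points in a five-participant dose level. It does not follow that participants are likely to disappear from the safety report. The gap is worth closing because one sentence closes it.

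**What to change.** Replace the source rule in SAP 9.2 with wording to this effect: *Summary tables use central results. Tests performed only locally (TEG, ROTEM) are summarised from local results, by device. Where a draw has no evaluable central liver result, the local result is used in the minimum and maximum post-baseline tables and in Table 14.3.4.5, classified against the local reference range, compared with a baseline on the same scale, and flagged.*

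Also:
- add TEG/ROTEM to the SAP table list;
- reconcile the last sentence of SAP 9.2.2 (collection only above 150% FIX:C) with Schedule of Activities note 19 (Day 0 and End-of-Study).

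This change does not bring in peaks from unscheduled visits. The rule in SAP 4 keeps those out of tables and would have to be considered separately.

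The cost is SAP wording and minor programming, since the SAP already plans to convert and list local results. The downside is some between-laboratory noise in the few flagged values.

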9.2.1. Hematology and Chemistry

Hematology and chemistry at baseline and post baseline visits will be summarized by dose group with descriptive statistics by visit and all will be presented in a data listing. Number of subjects (n), mean, standard deviation (SD), median, minimum and maximum will be presented for all change from baseline tables.

Each subject's laboratory values will be classified according to whether the test result is "low" (i.e., below the lower limit of normal [LLN]), "normal" (within the normal range), or "high" (i.e., above the upper limit of normal [ULN]). A shift table of minimum and maximum on-study records will be created by baseline classification. Additionally, the abnormality categorical data will be summarized in this shift tables comparing the results at the end of study visit at Week 52 with those at the baseline visit.

Liver function tests (LFT) will be similarly summarized. Baseline and post baseline visits will be summarized by dose group with descriptive statistics by visit and all be presented in a data listing. Number of subjects (n), mean, SD, median, minimum and maximum will be presented for all change from baseline tables. Each subject's laboratory values will be classified according to whether the test result is "low" (i.e., below the LLN), "normal" (within the normal range), or "high" (i.e., above the ULN]. The abnormality categorical data will be summarized in shift tables comparing the results at the end of study visit at Week 52, minimum post-baseline, and maximum post-baseline with those at the baseline visit.

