**3. OBJECTIVES, ESTIMANDS AND ENDPOINTS**

Objectives	Endpoints
Primary	

 
The primary objective is to evaluate the safety and tolerability of a single IV infusion of PF-06838435 in hemophilia B participants ≥18 years of age with ≤2 IU/dL [≤2 %] endogenous factor IX [FIX].
 
	
Clinically significant changes from baseline in the following:
 
 
Physical examination
 
Vital signs
 
Laboratory values
 
Incidence of drug-related adverse events (including inhibitor development)
 
FIX incremental recovery (time at maximum activity [Tmax] and percent recovery for FIX activity)
 
Immune response against AAV capsid protein
 
Immune response against hFIX transgene
 
 
For those individuals who develop hepatic transaminases (ALT and/or AST) elevation of approximately 1.5-fold or successively increasing during follow-up above baseline (or vector-derived FIX:C activity levels decline without evidence of FIX inhibitor, accompanied by rising IFN ELISPOTs on PBMCs) after PF-06838435 infusion, treatment with corticosteroids will be instituted. Alternative immunosuppressive

	
therapies will be considered if the initial corticosteroid treatments are not successful.
 
For any individual who reaches >150% vector-derived FIX:C activity levels after the infusion of PF-06838435, laboratory parameters of thrombotic potential will be assessed.

Secondary	

• The secondary objective is to characterize the kinetics of PF-06838435.

	

• Vector-derived FIX:C activity levels:

• Peak

• Steady-state

• FIX antigen levels

CCI
 	

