**Type of Participant and Disease Characteristics**

2. Have hemophilia B with  $\leq 2$  IU/dL ( $\leq 2\%$ ) endogenous FIX activity levels as documented from a certified clinical laboratory at the time of screening. If the screening result is  $> 2\%$  due to insufficient washout from the FIX product, then the severity of hemophilia B may be confirmed by documented historical evidence from a certified clinical laboratory demonstrating  $\leq 2\%$  FIX coagulant activity (FIX:C) or from a documented genotype known to produce clinically severe phenotype of hemophilia B;
3. Have had  $\geq 50$  prior exposure days (EDs) to any recombinant and/or plasma-derived FIX protein products based on historical data from participant's records/history;
4. a) Prophylaxis participants: Have had bleeding events and/or infusion with FIX products during the last 12 weeks, as documented in the participants' medical records; or
  1. b) On-demand participants: Have had  $\geq 4$  bleeding events in the last 52 weeks and/ or chronic hemophilic arthropathy (pain joint destruction and loss of range of motion) in one or more joints;
5. Have no history of hypersensitivity or anaphylaxis associated with any FIX or IV immunoglobulin administration;
6. Have no measurable FIX inhibitor as assessed by the central laboratory; or documented no prior history of FIX inhibitor after 50 EDs (family history of inhibitors will not exclude the participant) and no clinical signs or symptoms of decreased response to FIX administration;
7. Have acceptable laboratory values sampled at screening and reviewed prior to Day 0:
  - Hemoglobin  $\geq 11$  g/dL;
  - Platelets  $\geq 100,000$  cells/ $\mu$ L;
  - AST, ALT, alkaline phosphatase  $\leq 2x$  upper limit of normal (ULN);
  - Bilirubin  $\leq 3x$  ULN (Bilirubin levels above the laboratory's normal range are acceptable in individuals with a documented history or laboratory evidence of Gilbert's Disease);
  - Creatinine  $\leq 2.0$  mg/dL.

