9.3. Vital Sign Measurements

For vital sign evaluations, baseline is defined as the last non-missing evaluable assessment taken prior to PF-06838435 infusion. Vital signs include systolic and diastolic blood pressure, pulse, respiratory rate, and temperature. Summary tables will be presented by dose group for vital sign data, including systolic blood pressure, diastolic blood pressure, temperature, pulse rate, and respiration rate for subjects in the safety analysis set. Changes from baseline to each scheduled post-baseline visit will be presented. All vital sign data will be presented in a listing as well. Height and weight measurements taken at screening, Day 0 pre-vector infusion and EOS will also be included in this listing.

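### SAP 9.2.1 categorises laboratory values only as low, normal or high, so its shift tables cannot separate a Grade 4 transaminase rise from no change when baseline is above ULN

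*SAP*

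**What the plan says.** Protocol section 3 and SAP 3.2.1 make the primary endpoint "Clinically significant changes from baseline in the following", with laboratory values on the list. SAP 4.1 says there are no formal hypotheses, so the descriptive tables are the primary result.

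SAP 9.2.1 plans two kinds of laboratory table:

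- **Change tables by visit and dose group.** The number of subjects, mean, SD, "median, minimum and maximum will be presented for all change from baseline tables".
- **Shift tables** on three categories: below LLN, within range, above ULN. For liver tests, "The abnormality categorical data will be summarized in shift tables comparing the results at the end of study visit at Week 52"; the same sentence goes on to "minimum post-baseline, and maximum post-baseline with those at the baseline visit". Hematology and chemistry are handled in the same way.

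The SAP gives no numerical criterion for a clinically significant laboratory change. The protocol's graded toxicity scale (section 10.8, Appendix 8) enters through SAP 9.1.4: "A summary of TEAEs by toxicity grade". SAP section 4 keeps unscheduled visits out of summary tables and puts them in listings.

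**The concern.** Three categories record whether a value is out of range, not how far. The entry criteria make this matter. Protocol 5.1 accepts "AST, ALT, alkaline phosphatase" up to 2x ULN and bilirubin up to 3x ULN, so a participant can start in the high category and has no higher category to move to.

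Liver enzymes are where severity counts most in this trial. Grade IV transaminases judged at least possibly drug-related suspend enrolment (protocol 4.3.1), and a rise of about 1.5-fold over baseline is a treatment trigger (protocol 4.1.5). If the categorical table cannot show either level, the report will lack a simple count, taken from the measured values, of how many participants reached each grade.

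**Working it through.** The documents state no figure for this point, so there is none to reproduce. I applied the SAP's categories and the protocol's grades to the same ALT or AST values, in multiples of ULN.

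**Inputs**

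- SAP 9.2.1: high means above 1.0x ULN.
- Protocol Appendix 8, transaminases: Grade 1 is 2.5–2.9, Grade 2 is 3.0–4.9, Grade 3 is 5.0–10.0 and Grade 4 is above 10.0 times normal. I take normal to mean ULN, which the appendix does not say.
- Protocol 5.1: AST and ALT up to 2x ULN at screening. SAP section 4 defines baseline as the last usable value before infusion, so I assume baselines of 1.1 to 2.0x ULN.

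**Step 1: same value, two classifications**

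| Baseline (x ULN) | Post-baseline (x ULN) | SAP shift cell | Grade shift |
|---|---|---|---|
| 1.1, 1.5 or 2.0 | unchanged | high-to-high | 0 to 0 |
| 1.1, 1.5 or 2.0 | 2.6 | high-to-high | 0 to 1 |
| 1.1, 1.5 or 2.0 | 3.5 | high-to-high | 0 to 2 |
| 1.1, 1.5 or 2.0 | 6 | high-to-high | 0 to 3 |
| 1.1, 1.5 or 2.0 | 10.1 | high-to-high | 0 to 4 |
| 1.0 | 1.5 | normal-to-high | 0 to 0 |
| 1.0 | 10.1 | normal-to-high | 0 to 4 |
| 0.5 | 0.75 (1.5-fold) | normal-to-normal | 0 to 0 |

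Using the maximum post-baseline value brings the peak into the table, but only as high. The last row shows that Appendix 8 grades do not pick up a 1.5-fold rise within the normal range either, so that needs its own count.

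**Step 2: what the change tables show**

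Let one participant rise from 1.5 to 10.1x ULN at a scheduled visit while the other n − 1 do not change. The change is d = 10.1 − 1.5 = 8.6. Then mean = d/n, SD = d/√n, median = 0 and maximum = d.

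| n | Mean change | SD | Median | Maximum |
|---|---|---|---|---|
| 5 | 8.6/5 = 1.72 | 3.85 | 0 | 8.6 |
| 10 | 8.6/10 = 0.86 | 2.72 | 0 | 8.6 |
| 20 | 8.6/20 = 0.43 | 1.92 | 0 | 8.6 |

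The sizes 5, 10 and 20 are the steps for one dose level in protocol 4.1.3.1. For baselines of 2.0 down to 1.1 the maximum runs from 8.1 to 9.0. So the change table does reveal the case. It does not count cases: if two of 20 rose by 8.6, the maximum would still be 8.6.

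**Step 3: the other outputs**

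- **SAE tables.** Protocol 10.3.2 makes Grade IV transaminases reportable as SAEs when judged drug-related or possibly so. Attribution is still a judgment, and lower grades are covered only in part.
- **TEAEs by grade (SAP 9.1.4).** The change must first be recorded as an AE (protocol 8.2.5), and the grade is noted where applicable (protocol 10.3.3). A missing grade is shown as Grade 4, so that row can include ungraded events.
- **Table 14.3.4.5.** Its title selects participants by a 1.5-fold transaminase rise. The rises above are 5.05-fold (10.1/2.0) to 9.18-fold (10.1/1.1), so they would qualify. It covers transaminases only, and the SAP describes no breakdown by grade.
- **Listings and the by-subject figure of FIX:C and liver tests.** They show every case but summarise none.

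**Step 4: unscheduled values**

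Notes 3 and 14 to the protocol's Schedule of Activities use unscheduled visits for transaminase monitoring and for participants who need more frequent checks. SAP section 4 excludes those visits from summary tables. SAP 9.2 defines post-baseline as any assessment after infusion, but does not say whether this overrides section 4 for the minimum and maximum.

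**The case against.** The best defence is that severity is already well covered. The change tables carry the maximum. The worst liver events are mandatory SAEs, not left to discretion about whether to report them. TEAEs are tabulated by grade, and Table 14.3.4.5 picks up 1.5-fold rises. The protocol also uses clinically significant as a term of investigator judgment: section 10.3.1 says so for AEs, and section 8.2.5 requires documented review of every laboratory report. With about 20 participants and full listings, each case can be read individually. Finally, parts of Appendix 8 cannot be applied to measured values as written.

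Most of this stands, and it rules out stronger readings. A reader might infer that the SAP reports only mean changes, that a Grade 4 rise would go unseen, or that severity rests on discretionary AE reporting alone. The documents support none of these. A reader might also extend the point to vital signs, which have no shift or threshold table. But SAP 9.3 plans that "Changes from baseline to each scheduled post-baseline visit will be presented", SAP section 4 adds minimum and maximum for continuous variables, and most blood-pressure grades depend on therapy or persistence. A graded blood-pressure table is therefore not available from the readings alone.

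The gap that remains is narrower. No planned output, as described, counts participants by worst measured grade. The one categorical laboratory table discards severity, and it may also omit unscheduled peaks.

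**Conclusion.** The point holds for laboratory values. The shift tables in SAP 9.2.1 put an unchanged value and Grades 1 to 4 in one cell for transaminase baselines of 1.1 to 2.0x ULN, and put 1.5x and 10.1x ULN in one cell from a normal baseline. The case would still be visible in the maximum change (8.1 to 9.0x ULN in the example) if it fell at a scheduled visit, and in the SAE tables if judged at least possibly drug-related. What is missing is the count by grade.

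This rests on reading normal in Appendix 8 as ULN, on at least one participant starting above ULN for the high-to-high case, and on Table 14.3.4.5 being no more than its title says, since its layout is not shown. The documents do not say how many participants start above ULN. The normal-to-high case needs no such participant. The change is worth making because it concerns a primary endpoint and needs no new data. The present plan loses no data, since every value is listed.

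**What to change.** In SAP 9.2.1, keep the low/normal/high shift and add the following:

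1. Number and percentage of participants by worst post-baseline Appendix 8 grade, against baseline grade, by dose group. Include the tests that can be graded from measured values: transaminases, alkaline phosphatase, creatinine, hemoglobin and glucose. State that normal means ULN.
2. Worst-grade counts without a shift for tests graded relative to baseline (bilirubin and leukocytes).
3. Counts of participants with ALT or AST at or above 1.5x baseline, and above 10x ULN.
4. A sentence that minimum, maximum and worst-grade values use all post-baseline results, including unscheduled visits, overriding section 4 for these tables.

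Leave out blood-pressure grading. Before grading platelets or potassium, reconcile their units: Appendix 8 gives platelets per mL where protocol 5.1 uses cells per µL, and potassium in mg/dL.

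The cost is one derived grade variable and one added table, from data already collected.
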